3.1.1.5. Informed consent procedure

Informed consent will be required at the recruitment by trained research assistants, who will ensure it is administered appropriately. Two levels of consent will be sought from participants: consent to be screened for eligibility and if eligible, consent to participate in the study. A copy of the information sheet and consent form will be sent via e-mail to participants. Re-affirmation of consent will be required before participants complete the questionnaires pre-intervention, post-intervention, and at three months and six months.

In this study, as required by the UN CRPD, individuals' right to legal capacity (including the right to provide informed consent) will not be denied based on disability status. When necessary, participants will receive support tailored to their exigencies, to provide informed consent.

3.1.1.6. Interventions in the study

Intervention arm

Participants assigned to the intervention arm will be enrolled in the QualityRights online training, which aims to increase knowledge about the rights of people with psychosocial disabilities and change negative attitudes towards these persons and their role as rights holders. Furthermore, the training provides mental health professionals with the skills necessary to support people with psychosocial disabilities to advocate for their rights. The QualityRights online training includes five core modules: 1) Human rights; 2) Mental health, disability, and human rights; 3) The right to health and recovery; 4) Legal capacity and the right to decide; 5) Free from coercion, violence, and abuse [see Appendix 2 for further information about the online training topics]. Each module is composed of presentations, videos, interactive exercises, and forum discussions involving all participants. In the forum discussions, particular attention will be given to issues relevant to the Ghanaian context.

The discussions will be moderated by QualityRights trainers selected from a multidisciplinary team, including people with psychosocial disabilities, professionals working in mental health or the disability field, family members, and other local stakeholders.

Control arm

Mental health professionals assigned to the control arm will be enrolled in the WHO novel coronavirus 2019 online training series [see Appendix 4 for further information about the training topics and agenda]. This

trainings series provides a general introduction to COVID-19 and similar respiratory infections and information on what facilities and professionals should be doing to prevent and respond to COVID-19 cases. The training is similar in length to the WHO QualityRights training (12 hours 15 minutes vs. 19 hours) and is intended for health professionals and other stakeholders. To evaluate the integrity of this placebo intervention condition, we will collect information on potential enrollment in the online QualityRights training or other potential interventions at each assessment point.

3.1.1.7. Training of the trainers

Training of the QualityRights trainers was delivered by international WHO consultants with extensive expertise on QualityRights in February 2019. A multidisciplinary team from Ghana, including people with psychosocial disabilities, professionals working in mental health or the disability field, family members, and other local stakeholders, was trained during this event. In March 2019, this pool of new trainers delivered the QualityRights intervention to national and regional stakeholders. The new trainers were supervised by the WHO international consultants and received feedback on their ability to respect topics, time frames, and delivery modalities of the training.

3.1.1.8 Fidelity assessment

The local trial coordinator will participate in the QualityRights forum discussions at least once a week for quality control purposes and provision of detailed feedback. Model fidelity will be evaluated through a checklist investigating adherence to topics and time frames. The local trial coordinator will meet weekly with the project leaders for discussing feedback from the training and ensuring fidelity is respected throughout the entire period of training delivery.

3.1.1.9. Schedule of trial recruitment and participation

Enrollment into the study will commence in 2021. The schedule of enrollment and assessment follow the Standard Protocol Items: Recommendations for Interventional Trials (SPIRIT) Figure [Appendix 5] [180].

3.2.1.10. Collection of data and Assessment instruments

All the data will be collected through an online platform and made confidential according to the provisions that protect privacy in Europe (Articles 6 and 9 of EU Regulation No. 679) and Ghana (Data Protection Act, 2012).

- The **sociodemographic questionnaire** will include the following information:
 - I. Gender;
 - II. Age in years;
 - III. Educational attainment;
 - IV. Marital status;
 - V. Number of children;
 - VI. Religion;
 - VII. Profession;
 - VIII. Years working in a mental health service;
 - IX. Hospital and unit of work;
 - X. Region of residence;
 - XI. Main language;
 - XII. Family member(s) with a psychosocial disability;
 - XIII. Identification as “person with a psychosocial disability”.

In the case the WHO QualityRights intervention will be found to be not effective, these sociodemographic variables may be used to understand for which subgroups or under what circumstances the training did not work (although this work is outside the scope of the present proposal).

Primary outcomes

- The **World Health Organization’s Knowledge about the Rights of persons with psychosocial disabilities questionnaire** [Appendix 6] (16 items) was developed by WHO to assess knowledge about

the rights included in the UN CRPD. People with psychosocial disabilities had an active role in all the phases of the scale development.

- The **World Health Organization's questionnaire on the attitudes towards people with psychosocial disabilities as rights-holders** [Appendix 7] (17 items) was developed by WHO and includes three subscales: attitudes towards institutionalization and living independently in the community; attitudes toward mandatory treatment and coercion; attitudes toward people with psychosocial disabilities as decision-makers. People with psychosocial disabilities had an active role in all the phases of the scale development.

Secondary outcomes

- The **Practices related to substitute-decision making and coercion scale** [Appendix 8] (12 items) is a scale developed to measure the use of substitute-decision making and coercive practices in mental health units.
- The **Seclusion and Restraint Experience Questionnaire (SREQ)** [Appendix 9] [181] (44 items) was developed to measure emotional and ethical experiences linked to the use of seclusion and restraint among nurses. In this study, an abbreviated version of the scale (25 items), modified for the use among mental health providers, will be used to address seven domains: Negative Experiences, Positive Experiences, Experiences of Control, Experiences of Duty, Experiences of the Misuse of Seclusion and Restraint, Experiences of Seclusion and Restraint as Good Mental Health Practice, Experiences of Ethical Challenge.

The following data will also be collected:

- Information on the enrollment in the online WHO QualityRights training;
- Information on the enrollment in other potential interventions;
- Information on potential contacts with mental health professionals working in other units;
- Information on participants' satisfaction with the course.

The psychometric properties of the WHO's Knowledge about the Rights of persons with psychosocial disabilities questionnaire, the WHO's questionnaire on the attitudes towards people with psychosocial disabilities as rights-holders, and the Practices related to substitute-decision making and coercion scale (the questionnaire I plan to use in Aim 2) have not been tested in Ghana. A description of how we plan to evaluate these instruments' psychometric properties will be made in a separate document.

3.2.1.11 Blinding

Given the nature of the intervention, participants will not be blinded to their intervention arm. However, participants will not be informed of the study hypotheses and will know to which intervention arm they are assigned only after completing the pre-intervention assessment. Data analysts will have access only to anonymized data at the end of each assessment phase. Data will be presented for Group 1 and 2 without the data analysts knowing what 1 and 2 refer to in terms of intervention and control arms.

3.2.1.12 Contamination minimization

The risk of contamination is decreased by the cluster design. The intervention and control unit clusters, although in the same hospital, are distanced and physically separated. The chance of intervention cluster participants regularly meeting control cluster participants is negligible. Furthermore, participants will be asked not to share any information about the intervention they are assigned to with mental health professionals working in other units. Information on potential contacts with mental health professionals working in units allocated to a different arm will be collected at the follow-up interviews to assess the risk and level of contamination.

3.2.1.13 Problems anticipated

The goal of this study is to increase mental health professionals' knowledge about human rights, change their negative attitudes towards people with psychosocial disabilities and their role as rights holders, and change their practices related to substitute-decision making and coercion. The training itself poses no risk to participants. However, the trainers will be provided with skills on how to respond to any participant who may experience distress during the training.

3.2.1.14 Sample size and power calculation

The sample size calculation is based on the following assumptions: two-sided alpha level of 0.05 and power of 0.80. The study group decided that the ability to detect an effect size of 0.5 standard units at the total score at the WHO Organization's questionnaire on the attitudes towards people with psychosocial disabilities as rights-holders between the two groups would be worth finding. The unit of randomization will be the hospital units. The 28 hospitals unit clusters will be randomized with a 1:1 allocation ratio to the intervention or control arm. Based on data from previous cRCT in Ghana [182, 183], we assume a 20% loss to follow-up and ICC=0.05. Based on these assumptions, we calculated that 126 participants would be required in each arm group.

3.1.2 Analysis plan

3.1.2.1 Descriptive analyses.

Descriptive analyses will be conducted for the variables of interest (listed above). Univariate analyses will be used to examine continuous variables by assessing the mean, the median, and the spread of the data. Tabular analyses will be used to examine categorical variables by assessing frequencies. Missing data will be reported for each variable.

3.1.2.2 Approach to missing data.

Based on the descriptive analyses, the most appropriate strategy for accounting for missing data will be chosen. Although this approach does not provide definitive information, the level of missingness and the informativeness of the missing data (i.e., missing completely at random, missing at random, missing not at random) will be assessed by using graphical representation and a statistical assessment to determine if participants with missing data differ appreciably from those without missing data. When appropriate, inverse probability weighting will be used to account for missing data. Sensitivity analyses will be used to evaluate if the results obtained with the inverse probability weighting strategy differ appreciably from the results obtained with a listwise deletion strategy.

3.1.2.3 Main analyses.

An "intent-to-treat" analysis will be used to test the study hypotheses. The primary outcomes of interest will be 1) the change in knowledge about human rights and 2) the change in attitudes of mental health professionals towards people with psychosocial disabilities and their role as right-holders.

Since the data are continuous and longitudinal, linear mixed-effects (LME) regression models will be used to estimate average intervention effects while considering the shared variance of repeated measures and the clustered variance. Correlations arising from repeated measures will be accounted for by specifying an autoregressive covariance structure. Each outcome will be analyzed separately using LME. Time, intervention arm, and their interaction will be included in the model as fixed effects, while participants will be evaluated as random effects. Time will be entered as a categorical variable with levels corresponding to post-training and 3 AND 6 months. The effect of the intervention on the outcomes will be captured by the interaction between intervention and time, which will assess the mean difference between the intervention arms (QR e-training vs. control) in changes of outcomes over time within each group. Effect sizes will be reported as mean differences for each time point and intervention arm, with 95% confidence intervals.

(Random intercept with two group-level covariates and interaction).

Level 1:

$$Y_{ij} = b_{0j} + \varepsilon_{ij}$$

Level 2:

$$b_{0j} = \beta_{00} + \beta_{01}w_j + \beta_{02}t_j + \beta_{03}w_jt_j + b_{0j}^*$$

Combined:

$$Y_{ij} = \beta_{00} + \beta_{01}w_j + \beta_{02}t_j + \beta_{03}w_jt_j + b_{0j}^* + \varepsilon_{ij}$$

- Y_{ij} = attitudes
- β_{00} = "average mean" of units mean attitudes

- b_{0j}^* = difference between specific unit mean attitudes and “average mean” of units mean attitudes
- ε_{ij} = difference between individual attitudes and unit mean attitudes
- t_j = time (3 = at 6 months; 2 = at 3 months; 1 = post – training; 0 baseline)
- w_j = (1 = QR training; 0 control)
- β_{02} = regression coefficient for time
- β_{01} = regression coefficient for unit average attitudes when assigned to QR
- β_{03} = regression coefficient for the interaction of time and intervention

3.1.2.4 Secondary analyses.

Secondary outcomes will be the change in practices and experiences related to substitute-decision making and coercion. The change in practices will be evaluated at three months and six months, while the change in experiences will be evaluated both post-intervention and at three months and six months. These changes will be evaluated using the same methodology already described for the main analyses.

References

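### The autoregressive covariance fixed for the primary model can make the standard errors of the change contrasts too small or too large, and the protocol gives no figures to say which

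*Protocol*

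**What the plan says.** Section 3.1.2.3 (Main analyses) sets one linear mixed model for each primary outcome:

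- Covariance: "Correlations arising from repeated measures will be accounted for by specifying an autoregressive covariance structure". Order, variance pattern and time metric are not given.
- Random effects in the text: "participants will be evaluated as random effects". The displayed equation instead carries a random intercept for the unit.
- Mean model: "Time will be entered as a categorical variable with levels corresponding to post-training and 3 AND 6 months". The equation codes time as "3 = at 6 months; 2 = at 3 months", with 1 for post-training and 0 for baseline.
- Reporting: the effect is the arm-by-time interaction. "Effect sizes will be reported as mean differences for each time point and intervention arm, with 95% confidence intervals".

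Section 3.1.1.5 confirms the four assessments: consent is re-affirmed "before participants complete the questionnaires pre-intervention, post-intervention, and at three months and six months". Section 3.1.1.6 gives the course lengths as 19 hours (QualityRights) and 12 hours 15 minutes (control). The protocol does not give the calendar time over which the courses run, or say whether 3 and 6 months count from baseline or from the end of training. Section 3.1.2.3 names no alternative covariance, robust standard error or covariance sensitivity analysis.

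**The concern.** The primary result is a difference between arms in change from baseline. Its standard error depends directly on the correlation assumed between baseline and each later visit. A first-order autoregression on visit order ties the baseline-to-post-training correlation to the correlations between later neighbouring visits. There are two reasons to doubt that tie here.

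1. The first gap is the only one that contains a course meant to shift these scores, so baseline may correlate less with follow-up than the follow-ups do with each other.
2. The first gap may be shorter than the later ones, so baseline may correlate more with post-training.

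The first makes model-based standard errors too small, with intervals too narrow and a test level above 5%. The second makes them too large and costs power.

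**Working it through.** **The plan's own figure.** The protocol gives no covariance figure to reproduce. Its sample size does reproduce: 14 units per arm, effect 0.5 SD, ICC 0.05, and a t test on 26 degrees of freedom give power 0.797 with 6 per unit and 0.840 with 7. Then 7/0.8 = 8.75, rounded to 9, and 9 x 14 = 126 per arm. This does not depend on the repeated-measures covariance. With 20% loss, 9 x 0.8 = 7.2 per unit remain, for which the same calculation gives power 0.847. The 0.85 below is that reference point; the protocol's stated power is 0.80.

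**Spacing.** If 3 and 6 months run from baseline and post-training falls at month x, the gaps are x, 3 - x and 3, which cannot all be equal. If they run from the end of a training of length T, the gaps are T, 3 and 3, equal only when T = 3 months.

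**The restriction.** Participant intercept plus visit-order AR(1) gives covariance s_b^2 + s^2 x rho^|j-k|. Every adjacent pair then has correlation (s_b^2 + s^2 x rho)/(s_b^2 + s^2). The intercept adds the same amount to every pair, so it cannot separate the first gap from the others.

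**Method.** For each assumed true 4x4 covariance, the large-sample fit of the working covariance was found (minimum Gaussian Kullback-Leibler divergence). Its standard error for change from baseline was divided by the true one, with complete data and baseline as a level of time. With unit variances the true value is proportional to sqrt(2(1 - r)). Test level = 2(1 - Phi(1.96 x ratio)).

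*Worked case.* Baseline correlates 0.35 with every follow-up, and follow-ups correlate 0.70. The true value is sqrt(2 x 0.65) = 1.140. The fitted model gives 0.921. The ratio is 0.921/1.140 = 0.81, and the level is 2(1 - Phi(1.96 x 0.808)) = 0.113.

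All true correlations and visit months in this table are assumptions:

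| Assumed truth | Model SE / true SE at post-training, 3, 6 months | Test level at post-training |
|---|---|---|
| Equally spaced AR(1), 0.6 (check) | 1.00 / 1.00 / 1.00 | 0.05 |
| Break in both arms, 0.50 vs 0.60 | 0.94 / 0.96 / 0.96 | 0.067 |
| Break in both arms, 0.50 vs 0.65 | 0.90 / 0.94 / 0.95 | 0.077 |
| Break in both arms, 0.35 vs 0.70 | 0.81 / 0.90 / 0.92 | 0.113 |
| Break in both arms, 0.20 vs 0.75 | 0.74 / 0.88 / 0.94 | 0.148 |
| Break in intervention arm only, 0.35 vs 0.70 | 0.88 / 0.93 / 0.94 | 0.086 |
| Decay 0.8 per month, months 0, 1.5, 4.5, 7.5 | 1.22 / 1.02 / 1.00 | 0.017 |
| Decay 0.9 per month, same months | 1.25 / 1.04 / 1.00 | 0.014 |
| Either decay, months 0, 3, 6, 9 | 1.00 / 1.00 / 1.00 | 0.05 |
| 40% stable, 30% decaying, 30% noise, months 0, 1.5, 4.5, 7.5 | 1.04-1.05 at post-training, within 1-3% of 1 later | about 0.04 |

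**Power under smooth decay.** Starting from 0.85, power = Phi(1.036 + 1.96 - 1.96 x ratio) = Phi(2.996 - 1.96 x ratio). A ratio of 1.22 gives Phi(0.605) = 0.73, and 1.25 gives Phi(0.546) = 0.71. Starting from 0.80, Phi(2.802 - 1.96 x ratio) gives 0.66 and 0.64.

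**Autoregression on elapsed time.** This removes the spacing error but not the training break. With a participant intercept, the 0.35/0.70 case gives 0.86 at all three visits (level 0.094), and the 0.50/0.65 case gives 0.92 (0.071).

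**The case against.** A reader might infer that the autoregression is definitely indexed by visit number, that the visits are definitely unequally spaced, and that the primary test will therefore run above 5%. The documents support none of these as fact. The 0-3 coding belongs to the mean model, and a continuous-time autoregression is not excluded. The training duration and the origin of the follow-up visits are not stated, and spacing could be equal.

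Other points also stand. The control arm takes a COVID-19 course, which gives little reason for rights attitudes to re-order, and a break in one arm only does less harm. Questionnaire scores usually hold a stable component and noise, and then the participant intercept absorbs most of the misfit. The two mechanisms oppose each other: decay of 0.9 per month combined with a 20% break gives 0.95/0.99/1.00. A fallback structure or time metric may be set in a statistical analysis plan that is not shown.

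What remains is that the protocol itself commits to the autoregressive form. The participant intercept does not remove the restriction under visit-order AR(1), and elapsed-time autoregression leaves the training break untouched. Since the direction cannot be known in advance, there is no gain in imposing the restriction.

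**Conclusion.** The point holds as a conditional weakness, not as a demonstrated error. Over the assumed break range (0.2-0.5 against 0.6-0.75, both arms), the post-training standard error is about 6-26% too small. With a break of 0.35 vs 0.70 in the intervention arm only, it is about 12% too small. Under smooth decay of 0.8-0.9 per month with a 1.5-month first gap it is about 22-25% too wide; this shrinks to 4-5% with a large stable-plus-noise component and to nothing with equal spacing. Errors at 3 and 6 months are smaller in these cases.

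With complete data and categorical time by arm, only standard errors, intervals and p-values are affected. With the 20% loss that the protocol assumes, estimates can shift as well. The sample size of 126 per arm is not in question. The size and sign for this trial cannot be fixed from the protocol.

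**What to change.** In section 3.1.2.3, for both primary outcomes, replace the autoregressive structure and the participant intercept with an unstructured within-participant covariance over the four visits, alongside a unit-level random effect. This can match any covariance over the four visits, so the ratio above becomes 1.00 by construction.

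Name the fallback for non-convergence: a simpler structure with standard errors robust to covariance misspecification, clustered by unit, with a small-sample correction for 28 units. A heterogeneous Toeplitz structure is not a suitable fallback. It keeps one correlation for all adjacent visits, and in the 0.35/0.70 case it still gives 0.84 at post-training.

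The change to the text is small. An unstructured 4x4 matrix has 4 x 5/2 = 10 parameters against 3 for participant intercept plus AR(1), so seven more, with 2 x 126 = 252 participants and up to 252 x 4 = 1008 records. The downside is a small risk of non-convergence, which the fallback covers.

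### The primary test is an arm-by-time interaction, but the model has no random effect for how units change over time, so its error term omits between-unit variation in change although units are randomised

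*Protocol*

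**What the plan says.** Units are the randomised entity. Protocol section 3.2.1.14 states that "The 28 hospitals unit clusters will be randomized with a 1:1 allocation ratio" and, for planning, "we assume a 20% loss to follow-up and ICC=0.05".

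Section 3.1.2.3 defines both primary outcomes as changes, in knowledge and in attitudes, and sets out the model:

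- The effect: "The effect of the intervention on the outcomes will be captured by the interaction between intervention and time".
- The stated aim is to estimate this effect "while considering the shared variance of repeated measures and the clustered variance".
- The prose names participants as the random effects and asks for an autoregressive within-person structure. It names no random effect for units.
- The equation is labelled a random-intercept model. Its one random term besides the residual is b*_0j, defined as the "difference between specific unit mean attitudes and" the average of the unit means. It has no participant term and no unit-by-time term.

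Section 3.1.2.4 applies the same method to the secondary outcomes.

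**The concern.** When units are randomised, the arm effect on change has to be judged against how much units differ in their change. A participant intercept or a unit intercept that is the same at every visit subtracts out of that change. Neither model in section 3.1.2.3 therefore puts the relevant between-unit variation into the error of the interaction. The stated intention to account for clustering is not met for the one contrast that is tested. Listing both intercepts would not repair this.

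The validity of the confidence intervals and tests for both primary outcomes is at stake, and by section 3.1.2.4 for the secondary outcomes too. Five of the practices items (Appendix 8, items 8-12) ask about colleagues in the respondent's own unit, so shared unit-level change is plausible there.

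**Working it through.** **1. The plan's own sample size.** Inputs from section 3.2.1.14: "two-sided alpha level of 0.05 and power of 0.80"; "the ability to detect an effect size of 0.5 standard units"; 28 units, so 14 per arm; ICC 0.05; 20% loss. With m completers per unit, SE = sqrt(2 × [1 + (m − 1) × 0.05] / (14m)), and power is taken from a noncentral t with 28 − 2 = 26 df.

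- m = 6: power 0.797.
- m = 7: SE = sqrt(2 × 1.30/98) = 0.163, power 0.840.
- So 7 completers are needed; 7/0.80 = 8.75, rounded up to 9; 9 × 14 = 126.

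This matches "126 participants would be required in each arm group". The protocol does not state its method, but this route returns the figure exactly. It counts between-unit error on 26 df. After 20% loss, 9 × 0.8 = 7.2 per unit remain.

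**2. What cancels.** Write a score as unit effect + person effect + error. In a change from baseline, any part that is the same at both visits drops out: exactly with complete data, nearly so with dropout. What remains between units is the variance of their change, 2 × 0.05 × (1 − r), where r is the correlation of a unit's effect between visits. Neither the prose nor the equation has a term for it.

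**3. Size if participants are modelled.** Assumptions not in the protocol: total SD 1; ICC 0.05 applies at each visit; within-person correlation w = 0.5; r ranges from 1 to 0.

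- ICC of change = 0.05(1 − r) / [0.05(1 − r) + 0.95(1 − w)].
- Design effect DE = 1 + (m − 1) × ICC of change.
- Type I error = 2 × [1 − Φ(1.96/√DE)].

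Example, r = 0.5: ICC of change = 0.025/(0.025 + 0.475) = 0.05. With m = 7.2, DE = 1 + 6.2 × 0.05 = 1.31 and type I error = 8.7%.

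Simulated null trials, all REML fits with a z-test, are shown beside the formula:

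- A: participant + unit intercepts; 28 units of 9, four visits, 20% dropout, 1,000 trials per setting; post-training / 6 months.
- B: A's model plus an autoregressive structure; 28 units of 7, complete data, 1,500 trials per setting; range over the three follow-up visits.
- C: the displayed equation taken literally (unit intercept only); same data as A.

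| r | ICC of change | Formula, m = 7.2 / 9 | A | B | C |
|---|---|---|---|---|---|
| 1 | 0 | 5.0% / 5.0% | 4.5% / 4.8% | 4.2-5.8% | 0.4% / 1.0% |
| 0.8 | 0.021 | 6.5% / 6.9% | 6.4% / 6.8% | 6.6-7.3% | 0.9% / 2.0% |
| 0.5 | 0.050 | 8.7% / 9.8% | 10.1% / 9.5% | 8.8-10.4% | 1.8% / 3.1% |
| 0 | 0.095 | 12.0% / 14.0% | 13.0% / 13.5% | 11.3-11.9% | 4.1% / 4.7% |

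Letting w run from 0.3 to 0.7 and r from 0.9 to 0 gives about 5.5% to 19% by the formula.

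**4. Why C goes the other way.** Without a participant term, stable differences between people stay in the residual. With 7 per unit (98 per arm), the model SE is about sqrt(4 × 0.95/98) = 0.197. The true SE at r = 1 is sqrt(2 × 0.95/98) = 0.139. At r = 0 it is sqrt(2 × [0.10/14 + 0.95/98]) = 0.184. The model SE exceeds both.

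**5. Does the missing term repair it?** At r = 0.5 and w = 0.5, adding a unit-by-visit random effect to A brought 10.1% / 9.5% down to 5.4% / 6.1%, still with a z reference. Testing against between-unit variation in change on 26 df gave 4.9-5.2% at every r.

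**The case against.** **The size rests on figures the protocol does not give.** This stands. Neither the stability of unit effects nor the within-person correlation is stated, and with perfectly stable unit effects there is no inflation. The r = 0 row assumes that unit effects do not persist at all, although the same participants are reassessed. A reader might take the planning ICC of 0.05 to be the ICC of change, which would fix the answer at 8.7% without assuming r. The protocol does not say this: section 3.2.1.14 speaks of the total attitudes score.

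**The displayed equation makes the intervals too wide, not too narrow.** This also stands for that equation fitted literally. It is no safeguard: the conservatism comes from leaving out the participant effect that the prose requires, and it costs power.

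**The autoregressive structure changes the picture.** With a unit intercept and an autoregressive structure but no participant effect, type I error was 4.3-12.5% at post-training and 1.1-5.9% at 6 months. The prose asks for participant effects as well, and with both (column B) inflation appears at every follow-up visit once r falls below 1.

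**The notation is loose.** Time is written t_j, as though j could index a unit at a visit, which would make b*_0j a unit-by-visit effect. The definition of b*_0j, as one departure per unit, points the other way. The ambiguity is a further reason to rewrite the equation.

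**Degrees of freedom belong in an SAP.** Fair. The protocol's silence on the df method is not part of this point. The random-effects structure is written out in the protocol, and it is that structure which leaves the variation out.

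**Conclusion.** The point holds for the structure of the model. The primary effect is a difference in change between randomised units, and neither the prose nor the equation lets units differ in change, so the error of the tested contrast is wrong as written. Prose and equation also specify different random effects, and the two err in opposite directions.

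The size is conditional. With participants modelled, with or without a unit intercept, type I error runs from about 5% (r = 1) through 6-7% (r = 0.8) and 9-10% (r = 0.5) to 12-13% (r = 0), given ICC 0.05 at each visit, within-person correlation 0.5 and 7-9 per unit. With the literal equation it is about 0.4-5%.

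A reader might infer that an inflated false-positive rate is certain, or that intervals will be too narrow whichever model is fitted. The documents support neither. Nor is the sample size in question: 126 per arm reproduces.

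**What to change.** State one model, the same in prose and equation, with subscripts for unit, participant and visit. Give it random effects for participant, unit and unit-by-visit. Test the arm-by-visit contrasts against between-unit variation, with degrees of freedom based on the number of units (about 28 − 2 = 26; Kenward-Roger or Satterthwaite would do this). Alternatively, analyse unit-mean change by arm. Use the same method for the secondary outcomes.

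The cost is one more variance component and somewhat wider intervals than under a model without the unit-by-visit term. In simulated trials with 7 per unit, the ratio of empirical to model SE was 0.1497/0.1406 = 1.06 at r = 0.8, 0.1635/0.1425 = 1.15 at r = 0.5 and 0.1839/0.1459 = 1.26 at r = 0. Using a t reference in place of the normal adds a little more. No new data are needed and recruitment is unchanged.
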